^a Physical examinations will include assessment of the following body systems: abdomen; cardiovascular; ear, nose, and throat; eyes; hair and skin; lymph nodes; mental status; musculoskeletal; neurological; peripheral edema; and respiratory. Peripheral edema will be assessed using the semi-quantitative scale shown in Appendix B (Section 15.2.3).

^b Vital signs will always be measured prior to having blood drawn for laboratory evaluations. Blood pressure will be measured after patients have been sitting comfortably in a chair for at least 5 minutes prior to obtaining 3 readings using the same arm for each reading; the mean of the last 2 readings will then be recorded. Measurements of blood pressure intended to detect possible orthostatic hypotension will also be performed at each visit (see Section 9.6). For these measurements, blood pressure will be measured 3 times: 1 time after the patient has been in a supine position for 5 minutes, 1 time after the patient has been standing for 1 minute, and 1 time after the patient has been standing for 3 minutes. Weight, heart rate, temperature, and respiration rate will also be recorded. For patients <18 years of age, height will be measured every 6 months.

- ^c Includes clinical chemistry (sodium, potassium, chloride, bicarbonate, total protein, albumin, calcium, phosphate, glucose, cystatin, uric acid, BUN, creatinine [including calculation of eGFR], bilirubin [total, direct, and indirect], ALT, AST, ALP, gamma glutamyl transferase, creatine kinase, and amylase); lipid panel (total cholesterol, LDL [direct], HDL [direct], and triglycerides [direct]); hematology (red blood cells, hemoglobin, hematocrit, MCV, MCH, MCHC, platelets, WBC and WBC differential [neutrophils, eosinophils, basophils, lymphocytes, and monocytes, % and absolute]). All chemistry, hematology, and lipid analytes are shown in [Section 15.2.4](#).
- ^d NT-proBNP in patients ≥ 18 years of age only.
- ^e Urine total protein, creatinine, and microalbumin. The patient will collect the first morning void within 5 days prior to the visit and bring the sample to the site visit.
- ^f Patients ≥ 18 years of age will complete the KDQOL instrument, and patients < 18 years of age will complete the PedsQL QoL questionnaire. All patients will also complete the EQ-5D. If the questionnaires were NOT completed at Week 112 (ie, Visit 17), the patient should not complete them for the rest of the open-label extension.
- ^g Urine pregnancy tests will be dispensed to WOCBP to conduct pregnancy testing at home between study visits. Site will provide the patient enough tests to conduct pregnancy testing once per month until the next scheduled study visit and will contact these patients monthly to confirm that the pregnancy test has been performed and the results are negative. A positive urine pregnancy test will be confirmed by a serum test. At every visit and monthly, sites will verify that WOCBP are continuing to use highly reliable contraception methods.
- ^h Dispense investigational product. Patients will be instructed to take their investigational product at the clinic on the day of office visits. All other days, investigational product should be taken at approximately the same time each day, preferably prior to the morning meal. Patients will be instructed to swallow the tablets whole, and not to open, break, chew, crush, or split the tablet prior to taking. Patients will also be instructed to avoid drinking or eating anything that contains grapefruit, Seville oranges (bitter oranges often used as marmalade), or starfruit (carambola) throughout the study. The patient will be instructed to bring all investigational product and their original containers to the next clinic visit.

15.2. Appendix B: Supplemental Study Information

15.2.1. Concomitant Medication Considerations

A. While Taking Study Medication (ie, Day 1 Through Week 108)

1. Prohibited Medications While Taking Study Medication (ie, Day 1 Through Week 108)

Inhibitors of RAAS and the endothelin system:

- Patients who are taking any dose of these agents will undergo a 2-week washout period prior to randomization.
- Examples of RAAS inhibitors include (not all inclusive): ACE inhibitors, aldosterone blockers, ARBs, spironolactone, eplerenone, and aliskiren.
- Examples of the endothelin system include: bosentan, macitentan, and ambrisentan.
- Potassium-sparing diuretics (eg, amiloride, triamterene).
- Selected anti-diabetic drugs (thiazolidinediones and sodium-glucose cotransporter-2 inhibitors) should be avoided completely. Other anti-diabetic drugs (eg, metformin, glyburide) should be used in accordance with their guidelines for use in patients with impaired kidney function.
- Digoxin, amiodarone, or any other antiarrhythmic medications that may put the patient at higher risk due to the underlying disease.
- Amphetamines, amphetamine derivative agents, and prescribed weight loss medications including orlistat (eg, Alli[®], Xenical[®]).
- St. John's Wort or other hypericum-derived products.
- Strong CYP3A inhibitors. For a detailed list of these medications, see the P450 Drug Interaction Table at: <http://medicine.iupui.edu/clinpharm/ddis/main-table>.
NOTE: The Sponsor recognizes that in some cases concomitant use of these medications may be medically necessary (for example, azole antifungals for severe mycotic infections) and alternatives are either unavailable or inappropriate from a medical and safety perspective. In these cases, limited systemic exposure may be warranted; however, systemic use of strong CYP3A4 inhibitors should be avoided. In addition, a reduction in dose or temporary cessation of study medication and more intensive patient monitoring is recommended.
- The following medications are prohibited for 7 days prior to study visits and should be used with caution at other times during the study. Investigators must review each patient case individually and use clinical judgment.
 - Sulfamethoxazole/trimethoprim (eg, Bactrim[™], Septra[®]), cimetidine, pyrimethamine, cetirizine, cobicistat, probenecid, vandetinib, dolutegravir, ranolazine, dronedarone, ritonavir, and telaprevir cannot be used within at least 7 days prior to any visit at which eGFR is assessed.

- Fibrates.

See [Bullet B](#) for prohibited medications following discontinuation of study medication.

2. Medications to Be Used with Caution While Taking Study Medication (ie, Day 1 Through Week 108)

For any of the medications in this category, the dosage of study medication may need to be adjusted.

- Strong P-gp inhibitors:
 - In a clinical drug-drug interaction study, administration of cyclosporine increased sparsentan overall exposure by approximately 1.7-fold. Adjustment of study medication dosage may be needed during concomitant administration of a strong P-gp inhibitor.
 - The Investigator should actively look for potential AEs such as hypotension, hyperkalemia, or decline in eGFR, during the concomitant use of a strong P-gp inhibitor. See sparsentan dose reduction guidance in ([Section 8.3.2](#)).
 - Examples relevant to the study population include (not all inclusive): cyclosporine A, verapamil, quinidine.
- CYP2B6 substrates:
 - In a clinical drug-drug interaction study, administration of sparsentan for several days decreased exposure of bupropion, a CYP2B6 substrate, to approximately 66% to 68%.
 - Dosage adjustment of CYP2B6 substrate medications may be required during study medication treatment.
 - Examples relevant to the study population include (not all inclusive): bupropion, cyclophosphamide, ketamine, meperidine, methadone.
- Statins:
 - As CKD and proteinuria are associated with high cardiovascular risk, the use of statins may be warranted to reduce this risk.
 - Treatment should be initiated at the discretion of the Investigator (after consulting with the Medical Monitor, if needed), based on current guidelines for cardiovascular risk reduction. The lowest possible effective dose should be used.
- Non-steroidal anti-inflammatory drugs (NSAIDs):
 - NSAID use is discouraged during the study. Short-term (<1 week) or intermittent NSAID use is allowed, provided no doses are taken within 48 hours immediately preceding a study visit.
 - Aspirin at doses >325 mg/day is not allowed during the study.
- Steroids, calcineurin inhibitors, mycophenolate mofetil, and azathioprine doses must be stable for at least 30 days prior to screening and during the screening period.

Stable doses are defined as unchanged for the prior 30 days, with the exception of routine minor changes in calcineurin inhibitors. NOTE: It is recommended that systemic corticosteroid and/or immunosuppressive therapy for the treatment of FSGS be avoided for the duration of participation in the study. If, in the Investigator's opinion, systemic corticosteroid and/or immunosuppressive therapy is warranted, such intervention may be provided in addition to study medication at the discretion of the Investigator. Consultation with the Medical Monitor is recommended before starting interventional therapy, when possible. The medications in the categories above should be avoided or used with caution while taking study medication.

- Lithium:
 - Caution is required when combining lithium with inhibitors of RAAS, as it may enhance the actions of ACE inhibitors or ARBs.
- Warfarin:
 - Although no specific drug-drug interaction clinical studies have been performed, a theoretical potential exists for a drug-drug interaction between sparsentan and warfarin via protein binding displacement.
 - INR monitoring is recommended if warfarin is used concomitantly with study medication.

3. Additional Information

Additional medications potentially interacting with sparsentan (CYP3A inhibitors, P-gp inhibitors, CYP 2B6 substrates) can be found at:
<http://medicine.iupui.edu/clinpharm/ddis/main-table/>

B. Prohibited Medications Following Discontinuation of Study Medication

1. Non-treatment Period from Week 108 Through Week 112

- Irbesartan.
- Selected anti-diabetic drugs (thiazolidinediones and sodium-glucose cotransporter-2 inhibitors) should be avoided completely. Other anti-diabetic drugs (eg, metformin, glyburide) should be used in accordance with their guidelines for use in patients with impaired kidney function.
- Digoxin, amiodarone, or any other antiarrhythmic medications that may put the patient at higher risk due to the underlying disease.
- Amphetamines and amphetamine derivative agents.
- The following medications are prohibited for 7 days prior to study visits and should be used with caution at other times during the study. Investigators must review each patient case individually and use clinical judgment.
 - Sulfamethoxazole/trimethoprim (eg, Bactrim™, Septra®), cimetidine, pyrimethamine, cetirizine, cobicistat, probenecid, vandetinib, dolutegravir, ranolazine, dronedarone, ritonavir, and telaprevir cannot be used within at least 7 days prior to any visit at which eGFR is assessed.

- Fibrates.

C. Patients Who Have Permanently Discontinued Study Medication Prior to Week 108

- Irbesartan.
- The following medications are prohibited for 7 days prior to study visits and should be used with caution at other times during the study. Investigators must review each patient case individually and use clinical judgment.
 - Sulfamethoxazole/trimethoprim (eg, Bactrim™, Septra®), cimetidine, pyrimethamine, cetirizine, cobicistat, probenecid, vandetinib, dolutegravir, ranolazine, dronedarone, ritonavir, and telaprevir cannot be used within at least 7 days prior to any visit at which eGFR is assessed.
 - Fibrates.

D. While Taking Study Medication During the Open-label Extension Period (Starting at Week 112)

1. Prohibited Medications While Taking Study Medication (ie, During the Open-label Extension Period Starting at Week 112)

- Inhibitors of the RAAS
 - Examples include (not all inclusive) the following: ACEIs, aldosterone blockers, ARBs, and aliskiren
- Inhibitors of the endothelin system (bosentan, macitentan, and ambrisentan)
- Potassium-sparing diuretics (eg, amiloride and triamterene)
- Thiazolidinediones should be avoided completely. Other anti-diabetic drugs (eg, metformin and glyburide) should be used in accordance with their guidelines for use in patients with impaired kidney function.
- Digoxin, amiodarone, or any other antiarrhythmic medications that may put the patient at higher risk due to the underlying disease
- St. John's Wort or other hypericum-derived products
- Strong CYP3A inhibitors. For a detailed list of these medications, see the P450 Drug Interaction Table at: <http://medicine.iupui.edu/clinpharm/ddis/main-table>.
NOTE: The Sponsor recognizes that, in some cases, concomitant use of these medications may be medically necessary (eg,azole antifungals for severe mycotic infections), and alternatives are either unavailable or inappropriate from a medical and safety perspective. In these cases, limited systemic exposure may be warranted; however, systemic use of strong CYP3A4 inhibitors should be avoided. In addition, a reduction in dose or temporary cessation of study medication and more intensive patient monitoring is recommended.

2. Medications to Be Used with Caution While Taking Study Medication During the Open-label Extension Period (Starting at Week 112)

It is recommended that systemic corticosteroid and/or immunosuppressive therapy for the treatment of FSGS be avoided for the duration of participation in the study. If, in the Investigator's opinion, systemic corticosteroid and/or immunosuppressive therapy is warranted, such intervention may be provided in addition to study medication at the discretion of the Investigator. Consultation with the Medical Monitor is recommended before starting interventional therapy, when possible.

The medications in the categories below should be avoided or used with caution while taking study medication.

- Mineralocorticoid receptor antagonists (spironolactone and eplerenone) could be used at the discretion of the Investigator with appropriate serum potassium monitoring.
- Sodium-glucose cotransporter-2 inhibitors are allowed in the study at the discretion of the Investigator with appropriate monitoring of blood pressure and serum creatinine/eGFR. NOTE: When prescribing these medications, the Investigator should be aware of the fact that this class has not been tested and approved in pediatric patients and that the combination with immunosuppressive drugs is not recommended.
- Strong P-gp inhibitors
 - In a clinical drug-drug interaction study, administration of cyclosporine increased sparsentan overall exposure by approximately 1.7-fold. Adjustment of study medication dosage may be needed during concomitant administration of a strong P-gp inhibitor.
 - The Investigator should actively look for potential AEs, such as hypotension, hyperkalemia, or decline in eGFR during the concomitant use of a strong P-gp inhibitor. See sparsentan dose reduction guidance in [Section 8.3.2](#).
 - Examples relevant to the study population include (not all inclusive) the following: cyclosporine A, verapamil, and quinidine.
- CYP2B6 substrates
 - In a clinical drug-drug interaction study, administration of sparsentan for several days decreased the exposure of bupropion, a CYP2B6 substrate, to approximately 66% to 68%.
 - Effectiveness of drugs that are CYP2B6 substrates may be reduced, and monitoring of the effectiveness of CYP2B6 substrate medications, if possible, is recommended during treatment with study medication.
 - Examples relevant to the study population include (not all inclusive) the following: bupropion, cyclophosphamide, ketamine, meperidine, and methadone.

- NSAIDs
 - NSAID use is discouraged during the study. Short-term (<1 week) or intermittent NSAID, including aspirin use, is allowed. Chronic low-dose aspirin at doses ≤ 100 mg/day for cardiovascular protection is allowed during the study.
- Lithium
 - Caution is required when combining lithium with inhibitors of RAAS as it may enhance the actions of ACEIs or ARBs.
- Warfarin
 - Although no specific drug-drug interaction clinical studies have been performed, a theoretical potential exists for a drug-drug interaction between sparsentan and warfarin via protein binding displacement.
 - INR monitoring is recommended if warfarin is used concomitantly with study medication.

3. Additional Information

Additional medications potentially interacting with sparsentan (CYP3A inhibitors, P-gp inhibitors, and CYP2B6 substrates) can be found at:
<http://medicine.iupui.edu/clinpharm/ddis/main-table/>.

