6.2.2. Open-Label Extension Design

Patients may be evaluated for eligibility in the open-label extension using values from the Week 108 visit as screening assessments. Patients with an eGFR <30 (but >20) mL/min/1.73 m² will be eligible for participation in the open-label extension at the discretion of the Investigator, but will require close monitoring of eGFR and serum potassium (see [Section 7.2.2](#)).

For patients who agree to participate in the open-label extension and meet eligibility criteria (see [Section 7.2](#)), the Week 112 visit will also serve as the baseline visit for the open-label extension. Standard-of-care treatment (ACEI and/or ARB therapy) will be discontinued before the Week 112 visit. The final dose of an ACEI and/or ARB should be taken on the day before the Week 112 visit. At this visit, patients will sign a new informed consent (if not completed previously) for the open-label extension and begin taking open-label sparsentan. All Week 112 evaluations must be completed prior to the first dose of open-label sparsentan.

[figure not shown]
Patients who are taking 2 or 4 capsules of study medication (ie, 400 mg or 800 mg sparsentan or 150 mg or 300 mg irbesartan) at the end of the double-blind period will initiate treatment in the open-label extension at one-half the corresponding dose of open-label sparsentan for the first 2 weeks (ie, 200 mg or 400 mg sparsentan, respectively), then titrate to the target dose after confirmation of tolerability at Week 114. Patients who are taking 1 capsule of study medication (ie, 200 mg sparsentan or 75 mg irbesartan) at the end of the double-blind period will initiate treatment in the open-label extension at 200 mg open-label sparsentan and continue on that dose

throughout the open-label extension. For details regarding dose titration in the open-label extension, see [Section 8.1.2](#); for details regarding dose modifications, see [Section 8.3.2](#).

As in the double-blind period, additional antihypertensive agents are allowed during the open-label extension to maintain blood pressure $\leq 130/80$ mmHg (patients ≥ 18 years of age) or \leq the 75th percentile (patients < 18 years of age; [Banker 2016](#)), with the exception of those that inhibit the RAAS and endothelin systems (see [Section 15.2.1](#) for concomitant medication considerations).

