12.4. Demographics and Baseline Characteristics

Demographic data and baseline characteristics for the FAS, PP, and Safety Analysis Sets will be summarized by treatment group using descriptive statistics. Demographic data include sex, age (years), categorical age (<18 years and ≥18 years), race/ethnicity, weight (kg), height (cm), and calculated BMI. Baseline characteristics also include reproductive status (for females only), HbA1c, baseline eGFR, and current use of: steroids, calcineurin inhibitors, mycophenolate mofetil and other immunosuppressive agents, RAAS inhibitors (ie, ACE inhibitors, ARBs, aldosterone blockers, and aliskiren) prior to the 2-week washout, diuretics, additional antihypertensive treatments, and statins.

Likewise, demographic data and baseline characteristics for the OLEFAS will be summarized overall using descriptive statistics.

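### Open-label medication rules: D.1 prohibits aldosterone blockers without exception, D.2 conditionally permits spironolactone and eplerenone, and nothing says which rule takes precedence

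*Protocol*

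**What the plan says.** Four places in the protocol bear on this.

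- **15.2.1 D.1** lists medications prohibited while taking study medication from Week 112. Its first entry is inhibitors of the RAAS: "Examples include (not all inclusive) the following: ACEIs, aldosterone blockers, ARBs, and aliskiren". No exception for any aldosterone blocker follows.
- **15.2.1 D.2** covers the same period and lists medications for cautious use. Its lead-in reads "The medications in the categories below should be avoided or used with caution while taking study medication". The first item under it is "Mineralocorticoid receptor antagonists (spironolactone and eplerenone) could be used at the discretion of the Investigator", and the sentence goes on to require serum potassium monitoring.
- **15.2.1 A.1**, the double-blind list, shows how the protocol classifies the two drugs: "Examples of RAAS inhibitors include (not all inclusive): ACE inhibitors, aldosterone blockers, ARBs, spironolactone, eplerenone, and aliskiren".
- **6.2.2** allows antihypertensives to be added in the open-label extension to reach the blood-pressure target, "with the exception of those that inhibit the RAAS and endothelin systems", and refers the reader to 15.2.1.

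Protocol 4.1 supplies the safety context. It names hyperkalemia as a potential risk of sparsentan, attributes it to lower GFR and aldosterone inhibition, and says the risks are greater when kidney function is reduced.

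**The concern.** An investigator considering spironolactone or eplerenone in the open-label extension can cite D.1 for not using it and D.2 for using it. A monitor can cite D.1 to record a deviation and D.2 to record none. Counts of prohibited-medication deviations for this class then depend on which paragraph was consulted.

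The class is relevant to potassium in a population where potassium is already a concern. Under 6.2.2 and 7.2.2 the extension may admit patients with eGFR below 30 (but above 20) mL/min/1.73 m², who need close monitoring of eGFR and potassium. Double-blind entry required at least 30. Under 15.2.2, hyperkalemia that persists or recurs leads to permanent discontinuation of study medication. A conduct rule on such a class should have one reading.

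**Working it through.** There is no figure to reproduce. The check sets the texts side by side and asks whether any reading makes them consistent.

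**Step 1: same period, same patients.** Both D.1 and D.2 apply while study medication is taken in the open-label extension, starting at Week 112. The extension runs to Week 268, so the overlap is 268 − 112 = 156 weeks.

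**Step 2: do the two drugs fall under the D.1 prohibition?** There are two routes.

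| Route | Text | Result |
|---|---|---|
| As RAAS inhibitors | D.1 prohibits the class and marks its examples as not exhaustive; A.1 names both drugs as members of that class | Covered |
| As aldosterone blockers | 12.4 defines the class by a closed list: "RAAS inhibitors (ie, ACE inhibitors, ARBs, aldosterone blockers, and aliskiren) prior to the 2-week washout" | Of the four entries, only aldosterone blockers can hold them, so covered |

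A.1 lists spironolactone and eplerenone alongside aldosterone blockers, as if they were separate items. That weakens the second route but not the first, because A.1 still places all of them under RAAS inhibitors. Section 12.4 describes baseline medication and is not a conduct rule, so it is evidence of classification only.

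**Step 3: is the D.2 entry a permission?** Yes, a conditional one: investigator discretion, potassium monitoring, and a lead-in advising avoidance or caution. A conditional permission is still incompatible with an unqualified prohibition.

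**Step 4: is there a precedence rule or a stated exception?** None was found in 15.2.1 or 6.2.2. The protocol does write exceptions elsewhere:

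| Class | Double-blind list (A.1) | Open-label D.1 | Open-label D.2 | Consistent? |
|---|---|---|---|---|
| Strong CYP3A inhibitors | Prohibited, with exception note | Prohibited, with exception note inside the entry | Not listed as a cautious-use class | Yes |
| SGLT2 inhibitors | Prohibited | Removed | Allowed with monitoring | Yes |
| Spironolactone, eplerenone | Prohibited by name | Names dropped; aldosterone blockers and the RAAS class kept without exception | Allowed with monitoring | No |

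**Step 5: how far does it reach?** SAP 6.3.6 and Protocol 12.3.4 put every patient with at least one open-label dose in the OLEFAS, whatever deviations occurred. SAP 7.3 uses prohibited medication when deciding evaluability for the per-protocol and PK sets, not for the OLEFAS. The double-blind period has its own list (A.1), which prohibits both drugs without contradiction.

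**The case against.** The best reply is that D.2 is a specific exception to a general class ban. D.1 drops exactly the two names that A.1 carries, and D.2 then names both. A site looking up spironolactone by name for the open-label period finds only D.2. On this reading the words aldosterone blockers in D.1 are a drafting residue. This is plausible and may be what the sponsor meant. It does not remove the conflict: D.1 still bans the whole class with non-exhaustive examples, and it has no exception note like the one it gives strong CYP3A inhibitors.

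Other parts of the reply stand and limit the point.

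- A reader might infer that sites hold two flatly opposite instructions. D.2 is narrower than that, being conditional and under a caution heading.
- A reader might take 6.2.2 as an independent contradiction. It concerns only antihypertensives added for blood-pressure control and defers to 15.2.1, so it repeats the unqualified RAAS wording and does not add a second conflict.
- A reader might infer that open-label potassium and eGFR summaries are compromised because they mix users and non-users. Any discretionary rule would mix them. The summaries are descriptive (Protocol 12.12), and concomitant medications are summarized separately for the extension and listed by patient with dates and doses (12.9.1), so users can be identified.
- That sites will in fact differ is a prediction. The documents show only that the text allows it.
- Potassium is watched under either reading: D.2 requires monitoring, 15.2.2 calls for checks at each visit with stepwise actions above 5.5 mmol/L, and the Week 114 laboratory tests include potassium.

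**Conclusion.** The inconsistency holds. For the same drugs in the same period, D.1 prohibits and D.2 conditionally permits, and the protocol does not say which governs. The consequence is that one prescription can be classified as a deviation or as permitted use, for a class that bears on a named risk of the study drug.

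Its size is modest. It is confined to open-label conduct and deviation classification. The primary, surrogate and secondary double-blind analyses and membership of the OLEFAS are untouched. The number of patients who were or will be considered for these drugs is not given, so no rate can be attached.

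The conclusion rests on the protocol's own classification of spironolactone and eplerenone as RAAS inhibitors in A.1. It does not depend on whether the term aldosterone blockers was meant to include them, or on 6.2.2. No view is taken on whether the drugs should be allowed.

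**What to change.** Reconcile D.1 and D.2 so that mineralocorticoid receptor antagonists fall under one rule, or under a prohibition with an exception written into the D.1 entry itself, as is already done for strong CYP3A inhibitors. Align the RAAS wording in 6.2.2 by cross-reference to the reconciled text. Give monitors and data management a matching deviation code, and state how prescriptions already made under the present wording are to be classified, so that deviation listings are consistent across sites.

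Which rule applies is a clinical decision for the sponsor and is not proposed here. The cost is protocol wording and a line in the deviation guidance. Sample size, visits, assessments and statistical models do not change.
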